4.10.2 Primary Efficacy Variable(s)

Upper endoscopy for the examination of esophagus will be performed to confirm patient eligibility as well as the primary endpoint. The endoscopy examinations will be recorded on a video shot/digital images and these endoscopy videos/digital images will be evaluated by Investigator or endoscopy specialist, as required. Grade of erosive esophagitis due to GERD will be determined by the appropriately trained Investigator or endoscopist according to the LA classification (see Appendix 8 of protocol).

The endoscopy videos/digital images will be collected into a central database, with the appropriate anonymization. All videos and digital images will be centrally reviewed retrospectively. This review will include reassessment of the LA grading and other findings which may constitute exclusion criterion. The central reading evaluation will override the investigators' evaluations and will be used for all reporting and modelling. In case central reading evaluation is missing for a patient at screening or at week 4, due to poor video quality for example, the investigators' evaluations will replace the missing central reading. Hereafter, analyses based on central reading will consider central readings with imputations of local readings if missing.

Data obtained from patients deemed to have been ineligible for study enrollment following the retrospective analysis will be excluded from the per protocol analysis.

In the FAS analysis, the following subgroups of patients will be evaluated:

- the subgroup of patients classified as erosive with grade A/B or C/D at screening according to central reading
- the subgroup of patients classified as non-erosive (grade 0) at screening according to central reading.

A sensitivity analysis will also be conducted to present the healing results based on investigator or endoscopy specialist assessments (local reading). A second sensitivity analysis will be presented by category of LA Grade as assessed by the investigator and reclassified by central reading.

The primary objective of the study is to support dose selection for X842, through assessment of healing of erosive esophagitis due to GERD based on endoscopic assessment after 4 weeks of treatment. The aim is to identify the dose that will lead to having 85% of the patients have esophageal mucosa healing after 4 weeks of treatment.

Comparison of different doses of X842 to the active comparator arm (lansoprazole 30 mg) will not involve any formal statistical testing.

Lansoprazole treatment group will be analyzed descriptively.

The primary analysis will be performed for both the FAS and PPS as defined in Section 4.5.

In addition, the two subgroups, erosive esophagitis due to GERD LA grade C or D and erosive esophagitis due to GERD LA grade A or B, will be evaluated separately.

In the subgroup of patients with LA grade A or B, some of them were classified as A or B by investigator and thus are partial responders to PPI, but some of them were initially classified as C or D by investigator, and thus may not be partial responders to PPI. A subgroup analysis will be performed on the subgroup of patients with LA grade A/B according to their history of PPI treatment.

The rate of esophageal mucosa healing in the four X842 dose groups after 4 weeks of treatment (endoscopy performed at Visit 5) will be derived using the LA grading of GERD. If the grading is neither A, B, C or D, then the patient will be considered as having esophageal mucosa healing.

The rate of esophageal mucosa healing will be accompanied by 95% Clopper Pearson CI.

The primary analysis will involve dose-response modeling, evaluating a sequence of dose-response models for the healing rate including the Linear, Exponential, E_{max} , Sigmoid E_{max} and Logistic models (on logit scale).

The models will be compared in terms of model fit, and the target dose estimated as the dose providing the target effect of 85% healing rate from the best fitting model will be derived.

Several dose-response models will be fitted with the following factors:

- randomized study treatment (X842 25mg, X842 50mg, X842 75mg and X842 100mg)
- erosive esophagitis due to GERD (LA grade C or D / LA grade A or B)
- Center

Dose-Response Modeling

Multiple Comparison Procedure – Modeling

For all patients assigned to FAS, dose-response modeling will be performed using the multiple comparison procedure – modeling (MCP-Mod) approach [2, 3] with the following models in consideration:

1. Emax: $f(d) = E_0 + E_{max}d/(ED_{50} + d)$.
2. Sigmoidal Emax with $h = 3.5$: $f(d) = E_0 + E_{max}d^{3.5}/(ED_{50}^{3.5} + d^{3.5})$.
3. Logistic: $f(d) = E_0 + E_{max}/\exp((ED_{50} - d)/\delta)$.
4. Exponential: $f(d) = E_0 + E_1 \exp\left(\frac{d}{\delta}\right)$.
5. Linear: $f(d) = E_0 + \beta * d$.

Where:

- d is the dose level,
- ED_{50} the dose that gives 50 percent of the maximum effect,
- h the Hill coefficient,
- δ the rate of change for the logistic and exponential models,
- β is the slope for linear model,
- E_0 the basal effect at $d = 0$ and
- E_1 the scale parameter in the exponential model.

In the MCP-Mod approach, all statistically significant models listed above will be averaged in order to estimate the median dose for a given targeted response via inverse prediction along with associated 95% intervals using a bootstrap re-sampling method.

For the contrast test the following guesstimates will be assumed.

Model	Guesstimate
Emax	ED50 = 50
SigEmax1	ED50 = 50
Logistic, Exponential	$\delta = 200$

This MCP-Mod analysis will be performed using the R software (“DoseFinding” and “ggplot2” packages) [5], as follows:

1. MCP step:
 - a. Logistic regression model on the response variable with dose levels as categorical to obtain coefficients estimate and the relative covariance matrix.
 - b. “Mod” function of the “DoseFinding” package to perform the multiple contrast test (function “MCTtest”) part on the pre-specified candidate models
 - c. Significant candidate models will be evaluated by t-Test statistic and the adjusted p-value. Candidates for the modeling part will be selected with the following criteria:
 - i. Take the most significant candidate model ($p < 0.05$) or models if the t-Test statistic is equal.
 - ii. Stop if any of the model has not signal ($p > 0.05$).
2. Modeling step (Bootstrap):
 - a. $N = 1,000$ bootstrap samples of dose responses will be generated by a multivariate normal distribution with vector mean equal to the logit coefficients estimated on the MCP step and covariance matrix as its coefficients related covariance matrix.
 - b. For each Sample:
 - i. Fit the model by the “fitMod” function and select the best with goodness of fit based on the AIC criteria.
 - ii. Prediction of response probabilities based on the best model.
 - iii. Save the predicted values.
3. Compute the median of the bootstrap predicted values and 95% CIs.
4. Extraction of the dose at the target response probability with 95% CI.

Should there be three or more candidate model fail to fit on a bootstrap sample, the estimate for the bootstrap sample will be taken as unreliable. In case less than 70% of bootstrap sample estimates are taken as reliable an additional generalized linear mixed model (GLMM) analysis will be performed as

follows. A regression model with treatment (including Lansoprazole (QD) 30 mg group) and GERD category (with levels of A&B and C&D) as fixed and center as random effect will be fitted to binary data (logistic regression). Number of subjects with evaluable data and least squares mean estimates of response rates with accompanying 90% CIs will be provided for each dose level and for Lansoprazole (QD) 30 mg group using model estimates of the GLM described above.

The following summaries will be provided by study treatment group based on central reading results where some descriptive summaries on FAS will be presented on both subgroups of erosive and non-erosive patients at screening according to central reading. A subgroup analysis based on the LA grade A/B patients by prior PPI treatment will also be presented since some of the LA grade A/B patients were originally LA grade C/D patients as assessed by the investigator.

- Percentage of patients with esophageal mucosa healing after 4 weeks (FAS erosive/non-erosive/PPS)
- Percentage of patients with esophageal mucosa healing after 4 weeks by LA Grade (FAS subgroup of erosive patients/PPS)
- Percentage of patients with esophageal mucosa healing after 4 weeks by age (FAS subgroup of erosive patients /PPS)
- Percentage of patients with esophageal mucosa healing after 4 weeks by sex (FAS subgroup of erosive patients /PPS)
- Percentage of patients with esophageal mucosa healing after 4 weeks by center (FAS subgroup of erosive patients /PPS)
- Percentage of patients with esophageal mucosa healing after 4 weeks by H.Pylori at Baseline (FAS erosive/non erosive /PPS)
- Percentage of patients with esophageal mucosa healing after 4 weeks by Prior PPI Treatment (FAS Patients with LA Grade A/B)
- Bar-charts of percentage of patients with esophageal mucosa healing after 4 weeks (FAS erosive/non erosive /PPS)
- Bar-charts of percentage of patients with esophageal mucosa healing after 4 weeks by LA Grade (FAS subgroup of erosive patients /PPS)
- MCP-MOD: Testing a dose-response signal for Response Rate (FAS subgroup of erosive patients /PPS)
- Figure for dose-response shapes based on model-averaging method over all models in the candidate set (FAS subgroup of erosive patients /PPS)
- Results of the contrast test from the MCP-Mod analysis (FAS subgroup of erosive patients /PPS)
- Model parameter estimates of the individual dose-response models (FAS subgroup of erosive patients /PPS)

- Estimation of potential target dose based on model-averaging method over all models in the candidate set (FAS subgroup of erosive patients /PPS)

A sensitivity analysis based on local readings will be provided by study treatment group:

- Percentage of patients with esophageal mucosa healing after 4 weeks (Investigator or Endoscopy specialist reading) (FAS)
- Percentage of patients with esophageal mucosa healing after 4 weeks by LA Grade (Investigator or Endoscopy specialist reading) (FAS)

A second sensitivity analysis based on local readings and how those local readings were reclassified by central reading will be provided by study treatment group.

There will be 6 categories:

- Grade C/D that stayed C/D
- Grade C/D reclassified as A/B
- Grade C/D reclassified as grade 0 (non erosive) – if any
- Grade A/B reclassified as C/D – if any
- Grade A/B that stayed A/B
- Grade A/B reclassified as grade 0 (non erosive)

- Percentage of patients with esophageal mucosa healing after 4 weeks by Investigator LA Grade and its reclassification (FAS)

A listing of upper endoscopy results will be provided.

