5.3.2 Prior and Concomitant Medication and Therapy/Procedures

The patients are not allowed to concomitantly use any medication or therapy during the study likely to influence the outcome of this clinical trial. This includes:

- Agents affecting digestive organs
 - PPIs (e.g., omeprazole, pantoprazole, lansoprazole (except study medication), rabeprazole, esomeprazole, dexlansoprazole, dexrabeprazole, vonoprazan, etc.),
 - H₂ receptor antagonists (e.g., cimetidine, ranitidine, famotidine, nizatidine, niperotidine, roxatidine, lafutidine, ebrotidine, etc.),
 - muscarinic receptor 3 antagonists (e.g., atropine, scopolamine, hyoscyamin, ipratropium, tiotropium, pirenzepine, darifenacin, oxybutinin, refefenacin, etc.),
 - gastrointestinal prokinetic agents (e.g., metoclopramide, cisapride, domperidone, bromopride, alizapride, clebopride, itopride, cinitapride, mosapride, etc.),
 - anti-cholinergic agents (e.g., pirenzepine, telenzepine),
 - prostaglandins (e.g., misoprostol, enprostil, etc.),
 - antacids,
 - anti-gastrin agents (e.g., proglumide, oxethazaine, etc.).
- Medications that may affect the metabolism of X842 or linaprazan (cytochrome P450 [CYP] inhibitors and inducers) and medications that may be affected by X842 or linaprazan (substrates of CYP enzymes and drug transporters). For a comprehensive list, see Section 10.9 (Appendix 9),
- Medications contraindicated for use in combination with lansoprazole,
- Medications with reported drug–drug interactions with lansoprazole (warfarin, clopidogrel, ketoconazole, itraconazole, digoxin, tacrolimus, theophylline, methotrexate) and
- *H. pylori* eradication therapy (antibiotics along with PPI).

Patients are not permitted to undergo surgical intervention (e.g., fundoplication) for reflux disease or other antireflux procedures during study participation. Any planned major surgery within the duration of the study is exclusionary.

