6.6.1 Rescue Medication

All restrictions regarding the use of medications or therapies which are likely to influence study outcome are applicable for the entire duration of the study (please refer to Section 5.3.2 for not permitted medications).

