4.4.2 Protocol Deviations

All protocol violations will be judged as major or minor, taking composite effects of protocol deviations into consideration.

Major protocol deviations are defined as those deviations from the protocol likely to have an impact on the perceived efficacy and/or safety of study treatments. Therefore, patients for whom the clinical outcome is qualitatively affected by the protocol deviations will be excluded.

- Informed consent deviations
- Inclusion/Exclusion criteria deviations
- Disallowed medications
- AEs/SAEs deviations
- IP Administration/ study treatment deviations
- Procedures/tests deviations
- Visit schedule deviations
- Withdrawal criteria deviations

Protocol deviations and any action to be taken regarding the exclusion of patients or affected data from specific analyses are defined in the project-specific Protocol Deviation Specification.

The final classification and effect of each protocol deviation as well as the composite effect of a set of protocol deviations on analysis populations will be assessed prior to the database lock/unblinding on a Blinded Data Review Meeting [BDRM]. Results and population assignments will be summarized in a BDRM report which will be signed off by all relevant scientific experts.

The impact of major protocol deviations on the efficacy and/or safety results will be investigated by assessing the robustness of the study results and conclusions to the choice of analysis set, both including and excluding data potentially affected by major protocol deviations.

The following summaries will be provided:

- A summary of the number and percentage of patients with at least a major protocol deviation and by type of protocol deviation (Randomized Set).

The following listing will be provided:

- All major and minor protocol deviations (Randomized Set).

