4.5 Analysis Sets

For purposes of analysis, the following analysis sets are defined:

Population	Description
Enrolled	All patients who signed the ICF (including screening failures).

Population	Description
Randomized	All patients who have been randomized.
Full Analysis Set (FAS)	The full analysis set (FAS) will consist of all patients who have been randomized and received at least 1 dose of IMP. Patients will be analyzed according to randomized treatment (any randomized but not treated patient will be marked and reported as such).
Per Protocol Set (PPS)	The per protocol analysis set (PPS) will consist of all patients who have been randomized and completed the study without any major protocol deviations that are judged to compromise the analysis of the data. Mis-randomized patients will be removed from the PPS. All protocol violations will be judged as major or minor, taking composite effects of protocol deviations into consideration, excluding patients for whom the clinical outcome is qualitatively affected by the protocol deviations.
Safety Analysis Set (SS)	The safety analysis set will consist of all patients who have been randomized and received at least 1 dose of IMP. Patients will be analyzed according to the treatment actually received (in case this differs from randomized treatment).
PK Analysis Set (PKS)	The PK analysis set will consist of all patients who received at least 1 dose of IMP and have at least 1 measurement of plasma concentration of X842/linaprazan. Patients will be analyzed according to the treatment actually received (in case this differs from randomized treatment).

The efficacy summaries and analyses will be based on the **Full Analysis Set**, which is based upon the Intention-to-Treat principle.

For the primary efficacy variable(s), a sensitivity analysis will be performed on the **Per Protocol Set** to assess the robustness of the study conclusions to the choice of analysis population.

Secondary efficacy variable(s) will also be performed on the **Per Protocol Set**.

The PK summaries and analyses will be based on the **PK Analysis Set**.

The safety summaries and analyses will be based on the **Safety Analysis Set**.

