4.10.1.3 Handling of Dropouts or Missing Data

Primary endpoint:

The number and percentage of patients with missing data for the primary endpoint will be summarized by treatment group, by LA grade, overall and by major reason.

A patient data listing will be provided showing all patients with missing values for the primary endpoint. For these patients, the listing will provide important baseline characteristics, the recorded reason(s) for study discontinuation and the timing of study discontinuation.

In a primary analysis, missing healing results will be replaced with a non-responder approach. If there are more than 5% of patients with missing healing results, a sensitivity analysis will also be performed (tipping point method). Scenarios assuming probability of response 20%, 40%, 60%, 80% and 100% will be simulated. Fifty datasets for each probability will be generated, and for each one, an analysis will be conducted, Rubin rules will be used to combine the results.

Secondary endpoint: QOLRAD

Handling of missing values is described in section 4.10.3.1.

Secondary endpoint: mRESQ-eD

Handling of missing values is described in section 4.10.3.2.

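### Healing reached after prohibited acid suppression counts as X842 healing, and comparing the FAS erosive with the PPS cannot show how much this matters for the 85% dose

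*SAP*

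**What the plan says.** **Endpoint.** SAP 4.10.2 derives healing from the Visit 5 LA grade: "If the grading is neither A, B, C or D, then the patient will be considered as having esophageal mucosa healing". Section 3 of the SAP amendment restates this as grade 0 being healed. Neither text sets a condition on other acid suppression.

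**Missing data.** SAP 4.10.1.3: "In a primary analysis, missing healing results will be replaced with a non-responder approach". Section 4.5.6 of the amendment keeps non-response imputation for missing values. Neither extends it to observed results.

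**Prohibited drugs.** Protocol 5.3.2: "The patients are not allowed to concomitantly use any medication or therapy during the study likely to influence the outcome of this clinical trial". Its list includes PPIs, H2 receptor antagonists and antacids. Protocol 6.6.1, headed Rescue Medication, names no permitted drug: "All restrictions regarding the use of medications or therapies which are likely to influence study outcome are applicable" throughout the study.

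**Analysis sets.** The FAS keeps every randomized and dosed patient in the randomized arm (SAP 4.5). Amendment 4.5.2 makes the FAS erosive primary and the PPS supportive. SAP 4.4.2 lists disallowed medication among the major-deviation categories and says that "patients for whom the clinical outcome is qualitatively affected by the protocol deviations will be excluded". The details sit in a separate deviation specification, which is not among the documents, and the decisions are taken at a blinded review. The stated robustness check is to include and then exclude the affected data.

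**Target.** SAP 4.10.2 seeks the dose at which 85% of patients heal, read from the fitted curve over 25, 50, 75 and 100 mg BID.

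**The concern.** The trial exists to choose a Phase 3 dose by its own healing effect. A patient whose X842 dose is not working has two ways to deal with it. One who leaves before the endoscopy is counted as not healed. One who self-medicates with a prohibited acid suppressant and stays can be counted as healed. The plan treats these two kinds of failure in opposite ways and does not say that this is intended.

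The planned check does not separate them either. If users are mostly would-be failures, the FAS erosive turns some of them into successes, while the PPS removes failures from the denominator. Both rates rise, so the two sets can agree closely and both be too high for healing on X842 alone. No readable analysis counts users as not healed. Part of the sensitivity section in the amendment is redacted, so this can be said only of the visible text.

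**Working it through.** The documents state no figure on this point and the sample-size sections are redacted, so there is nothing to reproduce first. The only inputs they give are 48 patients per arm (Protocol 1.1), the four doses and the 85% target. All rates below are assumptions.

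**Notation for one arm.** *p* = healing on X842 alone; *u* = share using a prohibited acid suppressant, all of them otherwise unhealed; *h* = share of users who reach grade 0.

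- Users counted as not healed: *p*
- FAS: *p* + *u·h*
- PPS, if users are excluded: *p* / (1 − *u*)

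**Step 1, one arm.** Take 48 patients: 30 heal on X842 alone and 6 use a PPI, of whom 5 heal.

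- X842 alone: 30/48 = 62.5%
- FAS: 35/48 = 72.9%
- PPS: 30/42 = 71.4%

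The two planned sets differ by 1.5 points, yet they lie 10.4 and 8.9 points above the rate on X842 alone.

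**Step 2, target dose.** Assume *p* = 60/72/82/88.5% at 25/50/75/100 mg. Fit logit(rate) = *a* + *b*·dose by maximum likelihood to the expected counts and solve for 85%: dose = (logit 0.85 − *a*)/*b*. With users counted as not healed, *a* = −0.1446, *b* = 0.02195 and logit 0.85 = 1.7346. This gives (1.7346 + 0.1446)/0.02195 = 85.6 mg.

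Example of the inputs, with use of 12/8/4/2% and *h* = 0.8. FAS rates are 60 + 9.6 = 69.6, 72 + 6.4 = 78.4, 82 + 3.2 = 85.2 and 88.5 + 1.6 = 90.1%. PPS rates are 60/0.88 = 68.2, 72/0.92 = 78.3, 82/0.96 = 85.4 and 88.5/0.98 = 90.3%.

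| Use by dose (%) | *h* | FAS 85% dose (mg) | PPS 85% dose (mg) |
|---|---|---|---|
| none | – | 85.6 | 85.6 |
| 6/4/2/1 | 0.8 | 80.6 | 80.4 |
| 6/4/2/1 | 0.6 | 82.0 | 80.4 |
| 12/8/4/2 | 0.8 | 74.2 | 73.8 |
| 12/8/4/2 | 0.6 | 77.6 | 73.8 |
| 4/4/4/4 | 0.8 | 74.1 | 73.3 |
| 12/2/0/0 | 0.8 | 87.0 | 86.6 |
| 12.5/0/0/0 | 0.8 | 88.2 | 87.7 |

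**Step 3, why the direction can reverse.** In an unweighted straight-line fit to the four doses (mean 62.5, sum of squares 3125), the 25 mg point has weight 1/4 − 37.5(*x* − 62.5)/3125 on the fitted value at dose *x*. This weight is zero at *x* = 62.5 + 3125/(4 × 37.5) = 83.3 mg. Raising only the 25 mg point lowers the line above 83.3 mg, so a target above that dose moves up. The downward shift comes from use in the higher-dose arms as well.

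**Step 4, another curve.** Take a logit slope of 0.02 per mg, a true 85% dose of 75 mg, *h* = 0.6 and a weighted fit. Use of 5/3/1/0% gives 72 mg (FAS) and 71 mg (PPS). Use of 10/6/3/1% gives 66 and 62 mg. In the latter case the trend statistic falls from 2.87 to 2.34 (FAS) and 2.18 (PPS), so the signal needed at the MCP step also weakens.

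These fits omit center, LA grade, model selection and the bootstrap. They show direction and rough size only.

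**The case against.** **It is an estimand choice.** The SAP says that the FAS follows the intention-to-treat principle. Counting observed healing by randomized arm is consistent with that, and under a treatment-policy reading the FAS is not biased. This stands, and it is why the primary rule should stay. But the readable text never states that strategy for this event.

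**The size is assumed.** The documents give no use rate, no gradient by dose and no healing rate among users. If no user heals because of the added drug, the FAS is unaffected. If use is unrelated to who would heal, the PPS is unbiased for healing on X842. With use of 4/2/1/0% the shift is about 1 mg, while sampling error alone gives a simulated 95% range of about 65 to 127 mg under the same curve. All of this stands.

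**Not every user is affected as described.** Users still graded A to D remain not healed, users without a Visit 5 endoscopy are imputed as not healed, and exclusion from the PPS is a judgment made blind. This also stands.

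**Stronger readings that a reader might infer.** One is that the 85% dose is always pulled down because contamination gathers at 25 mg. Steps 2 and 3 refute this: use confined to 25 mg moves the target slightly up. Protocol 2.3 and 4.3 expect the lowest dose to be somewhat weaker than, or similar to, the comparator; they do not say that patients on it will take other drugs. Another is that low-dose symptom results are flattered as well. Nothing in the documents quantifies or demonstrates this.

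**Conclusion.** The gap is real but conditional. The healing rule takes no account of prohibited acid suppression, and including versus excluding users does not bound its effect when users are mainly would-be failures. On that condition, and if some users heal because of the added drug, both sets can overstate healing on X842 alone. The 85% dose is then usually biased downward: from about 86 mg to 81 mg or 74 mg in the two declining-use patterns. The second shift passes below the tested 75 mg level. With use confined to 25 mg the dose rises to about 88 mg.

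The documents do not show that any such bias occurred. If prohibited use before Visit 5 was negligible, a table by arm would show it and close the question. The case for acting rests on the low cost and on the lack of any readable analysis that could answer the question.

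**What to change.** 1. Keep the current FAS erosive rule as primary, and state how prohibited acid-suppressant use before Visit 5 is handled under it.
2. Tabulate, by arm, the use of prohibited PPIs, H2 antagonists and antacids between first dose and the Visit 5 endoscopy. Take the qualifying drugs from the Protocol 5.3.2 list, so that no new list is drawn up with treatment known.
3. Add one MCP-Mod target-dose sensitivity analysis on the FAS erosive, repeated on the FAS erosive PR, that counts these users as not healed.
4. Label it post hoc. Section 3 of the amendment says that it was written after unblinding, so the blinded review can no longer settle the matter.

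**Cost.** One derived flag and some extra analysis. Protocol 8.1.6 already collects drug names with start and stop dates, and SAP 4.8 already compares them with treatment initiation. The sensitivity analysis may count some genuine X842 healers with brief use as failures. Present it as a conservative bound on healing due to X842, not as a replacement for the primary result.

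### The MCP-Mod step misprints the Logistic, offers about two contrast shapes under five names, and contradicts itself on which models reach the 85% dose

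*SAP*

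**What the plan says.** All of the following is in SAP section 4.10.2.

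- The modelled doses are "randomized study treatment (X842 25mg, X842 50mg, X842 75mg and X842 100mg"; there is no placebo arm.
- Five candidates are listed: Emax, "Sigmoidal Emax with $h = 3.5", Logistic, Exponential and Linear. The Logistic is printed as "Logistic: $f(d) = E_0 + E_{max}/\exp((ED_{50} - d)/\delta" and the Exponential as "Exponential: $f(d) = E_0 + E_1 \exp\left(\frac{d}{\delta".
- ED50 is defined as "the dose that gives 50 percent of the maximum effect".
- The guesstimate table is introduced by "For the contrast test the following guesstimates will be assumed". It gives ED50 = 50 for Emax and for Sigmoid Emax, and a single delta = 200 on a row shared by Logistic and Exponential. No ED50 is given for the Logistic.
- Step 1c(i) of the MCP step reads "Take the most significant candidate model", with p < 0.05, allowing more than one only when the statistics are equal.
- Elsewhere the same section averages every significant model, picks the AIC-best model in each bootstrap sample, takes the target dose from the best-fitting model, and lists outputs averaged over the whole candidate set.

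The readable text of SAP amendment 01 changes none of this; parts of that amendment are redacted.

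**The concern.** This is the primary analysis, and its product is the dose predicted to heal 85% of patients. An MCP-Mod candidate set should cover distinct plausible shapes, so that the contrast test is robust and the choice among models carries information.

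Here two of the five formulas coincide as printed. The guesstimates make the remaining shapes hard to separate over 25 to 100 mg. One stated rule then keeps only the model with the largest statistic. If that rule governs, small sampling differences between nearly identical contrasts can decide which curve is carried forward. If another of the stated rules governs, the answer may differ, and the SAP does not say which takes precedence.

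**Working it through.** The plan gives no operating figure to reproduce, because the sample-size sections of both documents are redacted. Steps 1 to 3 use only the SAP's own formulas and guesstimates. Steps 4 and 5 need assumed healing rates.

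**1. Printed Logistic against Exponential.** Emax / exp((ED50 − d)/delta) = [Emax · exp(−ED50/delta)] · exp(d/delta). This is the Exponential with E1 = Emax · exp(−ED50/delta). At d = ED50 it gives Emax/exp(0) = Emax, which is 100% of Emax and not the 50% that the SAP's definition requires. Emax and ED50 cannot be estimated separately in this form.

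**2. Standard Logistic.** E0 + Emax/(1 + exp((ED50 − d)/delta)) gives half of Emax at d = ED50, so it agrees with the definition. Its contrast depends on both ED50 and delta, and the table supplies only delta.

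**3. Contrast shapes at 25, 50, 75 and 100 mg.** With equal variances, the optimal contrast is the centred and normalised mean vector.

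| Candidate | 25 | 50 | 75 | 100 |
|---|---|---|---|---|
| Emax (50) | −0.763 | −0.100 | 0.299 | 0.564 |
| Sigmoid Emax (50, h 3.5) | −0.763 | −0.118 | 0.353 | 0.528 |
| Exponential (200) = printed Logistic | −0.642 | −0.250 | 0.194 | 0.698 |
| Standard Logistic (50, 200) | −0.672 | −0.223 | 0.225 | 0.670 |
| Linear | −0.671 | −0.224 | 0.224 | 0.671 |

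The ED50 of 50 in the standard Logistic row is an assumption. Correlations:

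- Emax v Sigmoid Emax: 0.998.
- Exponential v Linear: 0.998.
- Standard Logistic v Linear: at least 0.9998 for any ED50 from 10 to 200.
- Between the two groups: 0.957 to 0.980.

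Unequal binomial variances (48 per arm; healing 65, 75, 85 and 90%, assumed) give 0.998, 0.998 and 0.961 to 0.980. Restoring the 1 + therefore does not create a third shape while delta stays at 200.

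**4. How informative is the largest statistic?** Assumptions: healing of 50, 60 or 70% at 25 mg rising to 90% at 100 mg along each distinct shape on the logit scale; 40 or 48 per arm; 4,000 trials per scenario; no filter on significance. The arm sizes come from the documents: 48 randomized per arm, and 200 evaluable over five arms, or 40 each. For 60% to 90% at 48 per arm:

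| True shape | Emax | Sigmoid | Exponential | Linear | Correct group |
|---|---|---|---|---|---|
| Emax | 30% | 34% | 24% | 12% | 64% |
| Sigmoid | 41% of picks are Sigmoid; Emax 24% | – | 22% | 12% | 66% |
| Exponential | 15% | 14% | 57% | 14% | 71% |
| Linear | 17% | 20% | 48% | 14% | 63% |

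(In the Sigmoid row, Emax is picked in 24% and Sigmoid in 41%.) Over all scenarios the correct group is picked in 58 to 75%, against 50% for a coin toss. The exact model is picked in 24 to 35% (Emax true), 40 to 45% (Sigmoid), 57 to 59% (Exponential) and 8 to 19% (Linear). The printed Logistic always ties exactly with the Exponential.

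**5. What the shape is worth in dose.** With healing of 60% at 25 mg and 90% at 100 mg, the logits are 0.405 and 2.197, and 85% is 1.735. The target lies (1.735 − 0.405)/(2.197 − 0.405) = 0.742 of the way up. Solving each shape gives about 64 mg (Sigmoid Emax), 69 mg (Emax), 81 mg (Linear) and 83 mg (Exponential). The full spread is 83 − 64 = 19 mg, against a dose spacing of 25 mg.

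**6. The selection rules side by side.** Step 1c(i) keeps one model. The averaging sentence keeps every significant model. The bootstrap step chooses by AIC, and the output list averages over all candidates. If only one model survives step 1c(i), there is nothing left to average, and AIC has nothing to choose among.

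**The case against.** The case against a stronger reading is good, and much of it stands.

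- **Selection is not random.** A reader might infer from the correlations that the chosen curve is pure chance. It is not: the right group is found more often than not. Mix-ups within a group move the 85% dose by only about 2 mg (81 v 83) or 5 mg (64 v 69). The larger moves, 12 to 19 mg, need a between-group error.
- **The collapse is confined to the contrast test.** The guesstimates serve that test only. ED50 and delta are refitted in the modelling step, so the fitted curves are not limited to two shapes. Correlated contrasts do not invalidate the test for a dose-response signal, and no loss of power has been shown.
- **The two Logistic defects are alternatives.** Under the printed formula ED50 only rescales and needs no guess. Under the standard formula the guess is missing but the duplicate disappears. The SAP's ED50 definition fits only the standard form, and package functions are named, so a dropped 1 + in typing or PDF reading is plausible. Either way the text needs correcting.
- **The bootstrap failure rule.** One might infer that "Should there be three or more candidate model fail to fit on a bootstrap sample" is distorted because Logistic and Exponential would fail together. That follows only if the misprint was coded literally, which the documents do not show.
- **Changing delta alone does not repair selection.** With Exponential delta = 30 and a standard Logistic (50, 200), simulation under a true Emax (65% to 88%, 48 per arm, assumed) still selected Emax in 27% of trials.

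What remains is the misprint or missing guess, the redundant contrasts, and the conflict between step 1c(i) and averaging.

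**Conclusion.** The point holds in a limited form. The printed Logistic is the Exponential and contradicts the SAP's own ED50 definition; read as the standard form, it lacks a guesstimate. On the per-administration scale of 25 to 100 mg the contrast test has about two shapes. Those statements rest on the SAP alone. If dose were coded as daily mg (50 to 200), Sigmoid Emax would separate from Emax (0.956) and about three shapes would remain.

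That choosing the largest statistic is weakly informative (58 to 75% correct between groups) and that the 85% dose ranges from 64 to 83 mg both depend on assumed healing rates. The contradiction between keeping one model and averaging all significant ones needs no assumption, and it is the part most likely to change the reported target dose. The SAP should be corrected on these points; the documents do not support a claim that the primary dose-response test is invalid.

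**What to change.** 1. Print the Logistic as E0 + Emax/(1 + exp((ED50 − d)/delta)) and give guesstimates for both ED50 and delta.
2. Replace step 1c(i) so that every significant candidate goes to the modelling step and is averaged, and bring the best-fit, AIC and output-list wording into line with that one rule.
3. Either set delta on the scale of 25 to 100 mg or drop the redundant shapes. As an illustration, Exponential delta = 30 lowers its correlation to 0.945 with Linear and 0.863 with Emax. A standard Logistic with ED50 = 50 still correlates 0.991 with Linear at delta = 20, so it needs a much smaller delta to add a shape. This makes the candidate set cleaner but does not by itself fix selection.
4. State in the report which formulas, guesstimates and selection rule were actually coded. SAP amendment 01 was written after unblinding, so label any changed candidate set as post hoc and show it beside the analysis as run.

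The drafting cost is a few lines of SAP text, one table and a few lines of R. More distinct contrasts raise the critical value slightly: in the simulation with Exponential delta = 30, power went from 0.877 to 0.867. The larger cost is that new shapes chosen now cannot claim to be prespecified.
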